N=40 adults (ages 18-50, approximately equal numbers of males and females) who are pre-screened to have mild-to-moderate levels of depression or who will serve as non-depressed/anxious controls will be recruited from community resources. Inclusion criteria are described in detail in the Human Subjects section. In brief, we will operationalize inclusion for the depressed group as any participant who scores >1.5 SD from normative levels on the Beck-Depression Inventory-II. Elevated trait anxiety on the Spielberger’s State/Trait Anxiety Inventory (STAI) will not disqualify inclusion (as depression and anxiety commonly co-occur). Any depression

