symptoms will not have to reach diagnosable levels of Major Depressive Disorder to qualify for the study. The non-clinical control group will have minimal symptoms on the BDI-II and State/Trait scales. Participants in each of these study groups then will be randomized into two conditions ($n=10$), each of which will receive 2 assessment/MRI appointments along with 6 sessions of guided practice/training in either 1) Re-interpretation or 2) Mindfulness ER techniques. If randomized into the CBT-based regulation training, subjects will be trained to use a cognitive strategy that instructs them to reappraise situations in positive or less negative ways. If randomized into the MBT-based regulation training, subjects will be trained to use a mindfulness strategy that instructs them to notice and accept their feelings without judgment or intent to act upon them. In both conditions subjects will be shown pictures of negative-affective stimuli and asked to use the strategy over and over again. These appointments will take place 'virtually' using a laptop computer that is set up at the participants house and is controlled remotely by Olin NRC staff. The training sessions will then be monitored by the research assistant via Skype, so that the participant can be given instructions and supervised while completing each session. "Training" in this context is conceptualized as the cumulative amount of practice, with the expectation that greater practice leads to greater mastery. Immediately after the first and sixth practice sessions, participants also will undergo fMRI so that brain function relative to that stage of practice can be assessed. In brief, training will be guided-practice sessions where examples of ER tactics are explained, modeled, then practiced with interactive discussion and feedback. To clarify, the primary outcomes for this pilot study will be fMRI-assessed brain function data, examined either to detect any changes in activation amplitude ("level of activity") in *a priori* ER-linked brain regions-of-interest (ROIs) (Table 1) or changes in the degree of functional connectivity among them. Secondary outcomes will be the BDI-II and STAI. Because we have a well-established infrastructure that includes many other datatypes useful for emotion-related neuroscience, we also will collect a variety of other individual-level data for exploratory analyses. By design, we propose to cast a wide net to collect information on the most relevant factors suggested by prior research to be explored. All data collection methods are described next, followed by a brief data analysis plan.

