Human Subjects Involvement and Characteristics All potential participants will undergo initial telephone screening to ensure they meet general inclusion/exclusion criteria. Qualified participants will then meet with study staff for informed consent. Following consent, they will undergo psychiatric interview and complete a battery of questionnaires to ensure none of the study exclusion criteria are met. At this point, participants will be randomized to one of the two ER training conditions (Reinterpretation or Mindfulness). The protocol requires 6 visits over three consecutive weeks at a time that is convenient for participants, and that they agree they can accommodate. We will attempt to structure an ideal schedule of appointments each week that follows a Mon/Wed, Tue/Thu, or Wed/Fri format. At each appointment, participants will undergo guided training in a specific ER tactic. Also, at the first and last MRI appointments, participants will complete a 60-minute fMRI

session. Prior to fMRI, participants will be tested for the presence of drugs and pregnancy (if female) through urinalysis.

Inclusion/Exclusion Criteria Inclusion: Ages 18-50, right-handed, a high-school level of education (11th grade attainment for 18 year-olds is acceptable if they haven't completed their final year yet), and \geq 8th grade English reading level to complete self-report evaluations (most are only available in English). Exclusion: Medical history that will exclude any potential participant includes head injury sufficient to have caused >30 minutes lost consciousness; past or current CNS disease (e.g., MS, epilepsy, tumor, etc.) or brain lesion identified by MR (structural MR scans will be reviewed by a radiologist for the presence of clinical neuropathology that may affect cognitive task performance); hypertension or juvenile-onset diabetes (current treatment with antihypertensives or insulin); current pregnancy (menstruating females will be tested). Psychiatric exclusion criteria include DSM-IV Axis I lifetime history of Bipolar disorder, PTSD, OCD, psychotic disorder, Tourette's disorder, or any Pervasive Developmental Disorder (e.g., Autistic disorder, PDD NOS, etc.); current DSM-IV substance dependence, ADHD, Conduct Disorder. Any participant who currently takes psychotropic medications will be excluded, even if psychiatric diagnostic criteria are not met.

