Data Safety and Monitoring Plan Whether or not this study should be considered a clinical trial is debatable. On the one hand, we will randomize participants into conditions and train them in how to regulate their emotions with separate tactics. Moreover, we are specifically recruiting a sample who will range from having mildly-elevated depression/anxiety symptoms to those who might meet DSM 5 diagnostic criteria for MDD or anxiety disorders. However, we purposefully are not employing any standardized treatment protocol in favor of using a “bare-bones” training-based intervention that provides guided practice on specific ways to regulate negative affect. We will not present this study opportunity to potential participants with any expectation that by the end of the study they will have achieved any relief for any mood or anxiety problems. Unless directed by the IRB to construct a more formal DSMP, we plan to follow standard Hartford Hospital adverse event reporting guidelines, which require reporting within 24 hours to the hospital Research Administration and Institutional Review Board any serious adverse event (i.e., serious injury or death related to the investigation) and within 7 days for minor adverse effects. However, if a DSMP typically is deemed appropriate by the IRB, we will formulate one that is appropriate to the perceived low-risk entailed in this experimental protocol.

References

1. Gross, J.J., *Antecedent- and response-focused emotion regulation: divergent consequences for experience, expression, and physiology*. Journal of Personality and Social Psychology, 1998. **74**(1): p. 224-37.
2. Gross, J.J., & Thompson, R.A., *Emotion regulation: Conceptual foundations*, in *Handbook of Emotion Regulation*, J.J. Gross, Editor 2007, Guilford Press: New York, NY. p. pp. 3-24.
3. Gyurak, A., J.J. Gross, and A. Etkin, *Explicit and implicit emotion regulation: a dual-process framework*. Cogn Emot, 2011. **25**(3): p. 400-12. **PMCID**: 3280343
4. Ochsner, K.N. and J.J. Gross, *The neural architecture of emotion regulation*, in *Handbook of Emotion Regulation*, J.J. Gross, Editor 2007, Guilford Press: New York, NY. p. 87-109.
5. Kalisch, R., *The functional neuroanatomy of reappraisal: time matters*. Neuroscience and Biobehavioral Reviews, 2009. **33**(8): p. 1215-26.
6. McRae, K., B. Ciesielski, and J.J. Gross, *Unpacking cognitive reappraisal: goals, tactics, and outcomes*. Emotion, 2012. **12**(2): p. 250-5.

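### Severity varies widely within the symptomatic group but is neither a randomisation stratum nor a model term, so with 10 per training a chance baseline gap can distort the pilot's estimates

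*Combined protocol and SAP*

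**What the plan says.** - **Who is in the symptomatic group.** APPROACH opens with "N=40 adults (ages 18-50, approximately equal numbers of males and females) who are pre-screened to have mild-to-moderate levels of depression" or who serve as controls. It then defines the depressed group as "any participant who scores >1.5 SD from normative levels on the Beck-Depression Inventory-II". That is a lower bound only; no upper BDI-II limit is stated. Elevated trait anxiety is allowed. A diagnosis is not required: "symptoms will not have to reach diagnosable levels of Major Depressive Disorder to qualify for the study". The exclusion criteria do not rule out MDD either. The Data Safety and Monitoring Plan describes "a sample who will range from having mildly-elevated depression/anxiety symptoms to those who might meet DSM 5 diagnostic criteria" for MDD or anxiety disorders.
- **How they are allocated.** APPROACH: "Participants in each of these study groups then will be randomized into two conditions", with n=10 in each. Human Subjects Involvement and Characteristics places the psychiatric interview and questionnaires first and then says "At this point, participants will be randomized to one of the two ER training conditions (Reinterpretation or Mindfulness"). Neither place names a severity stratum, a block scheme or minimisation. The gender balance under Sources of Materials is stated for the sample and not for the allocation.
- **How they are analysed.** The Analysis Plan specifies a 4 (group) × 2 (timepoint) mixed-effects ANOVA and names no baseline severity covariate. BDI-II and STAI, the secondary outcomes, are compared between baseline and the final session.

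**The concern.** The plan separates depressed people from controls before randomising, which deals with the coarsest severity difference. Inside the depressed group the range is still wide, and balance between the two trainings on that range is left to chance with 10 people on each side. BDI-II and SCID-5 status are already known when a person is allocated, so the information is available and unused.

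What is at stake is the Reinterpretation v Mindfulness estimate in symptomatic people. If one training happens to receive the more severe cases, part of any difference in change could reflect who was allocated and not which tactic was practised. BDI-II is the most exposed because it is both the severity measure and an outcome. The Power Analysis section says that one purpose of the pilot is to support effect magnitudes for later design, so a distorted estimate would be carried into that planning.

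**Working it through.** **Cell size.** 40 people / (2 study groups × 2 trainings) = 10 per cell, which agrees with APPROACH. The symptomatic comparison is therefore 10 v 10; each training has 20 people overall.

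**Baseline gap with the planned allocation (10:10 assumed).** In units of the within-group SD, the difference between the two cell means has standard error √(2/10) = 0.447. The chance of an absolute gap above t is 2 × [1 − Φ(t/0.447)]:
- t = 0.3: 50%
- t = 0.5: 26%
- t = 0.8: 7%

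The 0.5 SD threshold is a chosen yardstick; the plan sets none.

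**Split of diagnosed cases.** The documents do not say how many of the 20 will meet criteria, so a range is assumed. With K diagnosed and 10 drawn for one training (hypergeometric), the chance that the trainings differ by 4 or more diagnosed people is:
- K = 6 or 14: 14.1%
- K = 8: 17.0%
- K = 10: 17.9%

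**What a 0.5 SD gap does to an outcome.**
- BDI-II change: with no training effect, equal variances and baseline-to-final correlation ρ, the expected spurious difference in change is 0.5 × (1 − ρ). For ρ from 0.5 to 0.8 (assumed) this is 0.25 to 0.10 SD.
- fMRI change: if severity correlates r with change, the shift is 0.5 × r in SDs of change. For r = 0.3 (assumed) it is 0.15 SD, against a 10 v 10 standard error of 0.447 SD. For r = 0 it is nil.

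**Effect of one binary stratum.** I simulated allocations of 20 people in permuted blocks of randomly varying size 2 and 4 within two BDI-II strata, allowing unfilled last blocks. The chance of a gap above 0.5 SD was:

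| Scores | Cut | P(gap > 0.5 SD) |
|---|---|---|
| Normal | none (as planned) | about 26% |
| Normal | median | about 8 to 9% |
| Normal | 80th percentile | about 14% |
| Strongly skewed | none (as planned) | about 25% |
| Strongly skewed | median | about 13% |

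Fixed blocks of 2 give nearly the same balance (about 7.5% and 13% at the median), so varying the block size costs little.

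**Precision for fMRI change.** Removing all linear severity imbalance multiplies the standard error by √(1 − r²). That is 0.954 at r = 0.3 (about 5% smaller) and 0.866 at r = 0.5 (13% smaller). A median split of a normal score captures 2/π = 0.637 of that variance: √(1 − 0.637 × 0.09) = 0.971 (3%) and √(1 − 0.637 × 0.25) = 0.917 (8%). All are before the loss of 1 df. A cautious summary is a standard error 4 to 8% smaller for r between 0.3 and 0.5 (assumed).

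**The case against.** Much of the case against stands.

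- **A reader might infer that the comparison is biased or the test invalid.** It is neither. Randomisation protects the test, and the ordinary standard error already includes this chance variation. The primary outcome is within-person change, so severity matters only as far as it predicts change.
- **A reader might infer that severity is the strongest driver of training response.** No section says so. Synthesis and Formulation names a different candidate: individual differences in brain function before training.
- **A reader might infer that the key planned test is affected.** The Analysis Plan states no symptomatic-only contrast of the two trainings, and its baseline-to-final BDI-II and STAI comparison is not described as a comparison between trainings. The point applies to such a contrast if it is made.
- **The range has limits.** Pre-screening is described as mild-to-moderate, and current psychotropic medication and several diagnoses are excluded. This narrows the spread, but no upper BDI-II limit is given.
- **Severity is not wholly ignored.** Clinical Assessment and the supplemental analyses plan exploratory use of the psychological measures, BDI-II included. Adjustment afterwards is also possible, so imbalance is not beyond repair.
- **Stratification has its own risk.** In fixed blocks of 2, every second allocation can be predicted by anyone who knows the one before. Staff deliver the training, and no concealment is described. The fix therefore uses varying blocks.

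What survives is that small cells are where chance imbalance is largest, the data needed to limit it are already in hand, and neither the allocation nor the core model uses them.

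**Conclusion.** The concern holds as a modest one. With 10 v 10 in the symptomatic group, about one allocation in four would leave the trainings more than 0.5 SD apart on BDI-II at entry, and nothing in the allocation or the core model addresses this. The 26% rests on a 10:10 split and approximately normal means. The diagnosis-split figures rest on assumed counts, and the effects on outcomes rest on assumed correlations that the documents do not give. The possible distortion is clearest for a comparison of BDI-II change. For fMRI change it is small unless severity predicts change fairly strongly. Nothing here supports a claim of systematic bias or an invalid analysis. In a pilot, this is a change to consider.

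**What to change.** - **Allocation (APPROACH; Human Subjects Involvement and Characteristics).** Stratify the symptomatic group's randomisation by one binary factor known before allocation: either a BDI-II cut fixed in advance near the expected middle of the group, or SCID-5 current MDD/anxiety disorder yes/no. Use concealed permuted blocks of randomly varying size 2 and 4. Leave the control group's randomisation as it is.
- **Analysis (Analysis Plan).** In any contrast of the two trainings within the symptomatic group, include that stratum or, preferably, continuous baseline BDI-II.

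**Cost.** One more randomisation list and 1 df; no added participants, visits or assessments. Arms will usually be 10:10 or 11:9 and rarely 12:8. If severity does not predict change, the extra term loses a little precision. A badly placed cut reduces the gain without removing it. If the allocation cannot be changed, pre-specifying baseline BDI-II as a covariate would recover much of the benefit for the same 1 df.
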